5.2.3. Mixed Models Repeated Measures (MMRM) Analysis

The MMRM model will include participant as a random term, and baseline, time (as a factor), baseline-by-time interaction, treatment and treatment-by-time interaction as fixed terms in the model. An unstructured covariance matrix will be fitted to the repeated times within subject (other covariance matrices will be considered if necessary), and the Kenward Roger approximation will be used for estimating degrees of freedom. Additional terms may be fitted in the model (eg, type of therapy [ie, platinum or not], type of cancer), as appropriate.

Least-squares (LS) means (and 90% CIs) and LS mean differences versus placebo (and 90% CIs, and p-values for primary and selected secondary/tertiary endpoints), at each timepoint, will be provided. No adjustments will be made for multiplicity. In addition, profile plots of the LS means and differences (and 90% CIs for both) will be produced over time, with a separate line for each treatment group.

Standard SAS output will be provided to support the statistical summary table for the analysis model but will not be included in the CSR.

Example SAS code is provided in Appendix 4.

Statistical Model Diagnostics

The presence of outliers will be investigated for this model. An outlier will be defined as any response data value with a studentized (conditional) residual greater than 3, or less than 3. A listing will be presented of any participants meeting these criteria and will be included with standard SAS output. The assumptions of normality will be verified graphically using

residual plots. For each fitted model, a set of conditional studentized residual plots will be produced, including residual plot, histogram of normality, quartile-quartile (QQ) plot and summary of fit statistics. The residual plots will not be included in the CSR.

If there are outliers or major deviations from normality, then the effect of these on the conclusions may be investigated through alternative transformations and/or analyses excluding outliers. Justification for any alternative to the planned analysis will be given in the report of the study.

5.2.4. Bayesian Emax Model

The Bayesian four-parameter Emax model will use dose as a continuous variable. The model structure will take the form:

$$CFB = E_0 + \frac{E_{max}*dose^{Hill}}{ED_{50}^{Hill} + dose^{Hill}}$$

 E_0 is the placebo response, dose is the randomized dose (placebo dose = 0), E_{max} is the maximum effect, ED_{50} is the dose producing 50% of the maximum effect and Hill is the slope parameter. The model will utilize a Bayesian methodology approach as described in Appendix 5.

Estimates of the model parameters of E_0 , E_{max} , ED_{50} and Hill and their 95% credible intervals will be produced to support the statistical summary table for the analysis model but will not be included in the CSR.

The posterior medians and 90% credible intervals (5th and 95th percentiles of the relevant posterior distribution) will be reported for each randomized dose (including placebo) and their differences relative to placebo. Plots of the posterior medians and differences (including credible intervals for both) will be produced versus dose. No adjustments will be made for multiplicity.

If the E_{max} model cannot be fitted to the data, or the data do not support a dose-response, the model may be simplified, or the analysis may not be performed.

5.2.5. Analysis of Covariance (ANCOVA)

The ANCOVA model will include baseline and treatment as fixed terms in the model. Additional terms may be fitted in the model (eg, type of therapy [ie, platinum or not], type of cancer), as appropriate. LS means (and 90% CIs) and LS mean differences versus placebo (and 90% CIs) will be provided. No adjustments will be made for multiplicity. In addition, plots of the LS means and differences (and 90% CIs for both) will be produced.

Standard SAS output will be provided to support the statistical summary table for the analysis model but will not be included in the CSR.

Example SAS code is provided in Appendix 4.

Statistical model diagnostics will be assessed in a similar way to that described in Section 5.2.3.

5.2.6. Cumulative Incidence Plots

Cumulative incidence plots will be produced based on the time to the event of interest (starting from the time of start of dosing on Day 1) for each treatment group separately, all treatments on the same plot. This will be based on plotting the cumulative incidence function (with no competing risks), which will be presented as a percentage on the y-axis. Participants who discontinue from the study or from study intervention will be censored at the associated discontinuation date. The number of participants at risk at each timepoint may be included.

Example SAS code is provided in Appendix 4.

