# 7. DISCONTINUATION OF STUDY INTERVENTION AND PARTICIPANT DISCONTINUATION/WITHDRAWAL

#### 7.1. Discontinuation of Study Intervention

It may be necessary for a participant to permanently discontinue study intervention. Reasons for permanent discontinuation of study intervention may include the following:

- Progression of underlying disease such that the investigator no longer considers participation appropriate, or of potential benefit to the participant.
- Hospitalization that in the opinion of the investigator would render continued participation unfeasible.
- If a participant experiences Grade 3 AEs judged by the Investigator as related to randomized study intervention, the study intervention will be temporarily discontinued until the treatment-related AEs return to Grade 2 (or less). If the treatment-related AEs return to Grade 2 (or less) or resolve within 4 weeks, continuation of dosing with study intervention may be considered. If these AEs do not return to Grade 2 (or less) within 4 weeks, and after discussion with the sponsor, the participant will be permanently discontinued from the study intervention.

- If a participant experiences Grade 4 AEs judged by the Investigator as related to randomized study intervention, the participant will be permanently discontinued from the study intervention.
- Severe allergic reaction to study intervention.
- Intent to become pregnant or pregnancy confirmed by b-hCG testing.
- Drug-induced liver injury as described in Section 10.6, Appendix 6.

Note that discontinuation of study intervention does not represent withdrawal from the study. If study intervention is permanently discontinued, the participant should remain in the study to be evaluated for follow up. All cases of planned or potential discontinuation of study intervention should be discussed with Sponsor before classifying a subject as 'Discontinued from Study Intervention' and completing an Early Termination visit. See the SoA for data to be collected at the time of discontinuation of study intervention and follow-up for any further evaluations that need to be completed.

In the event of discontinuation of study intervention, it must be documented on the appropriate CRF/in the medical records whether the participant is discontinuing further receipt of study intervention or also from study procedures, posttreatment study follow-up, and/or future collection of additional information.**Follow-Up:** 

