3.4.12. Survival status at end of Part A

The survival status at the end of Part A will be recorded for each participant. End of Part A is considered Week 12 for all participants (regardless of whether they enter the optional Part B or not).

The time (days) to death during Part A (up to Week 12) will also be calculated for each participant.

3.4.13. Response as defined by a ≥3.5% increase from baseline in body weight at Week 12

Additionally, response, as defined by a ≥3.5% increase from baseline in body weight at Week 12, will be defined as having two levels: 'Response' and 'Non-response'. The former will be based on participants having a ≥3.5% increase from baseline in body weight at Week 12. Otherwise, participants will be classed as having a 'Non-response'. Participants with an intercurrent event of premature discontinuation of study intervention, prohibited procedure/medication or inadequate compliance prior to Week 12 will have their Week 12 value censored (if not missing). Missing or censored values at Week 12 will be imputed as described in Section 5.3.1. Participants who die during the study will be classed as having a 'Non-response' after imputation. This endpoint will be calculated similarly for Week 4 and Week 8.

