PK	All participants randomly assigned to study intervention and who take at least 1 dose of ponsegromab and in whom at least 1 PK concentration value is reported.
PD	All participants randomly assigned to study intervention and who take at least 1 dose of study intervention and in whom at least 1 PD (GDF-15) concentration value is reported.
Immunogenicity	All participants randomly assigned to study intervention and who take at least 1 dose of ponsegromab and in whom at least 1 ADA result is reported.

For participants who discontinue study intervention, the date of discontinuation of study intervention is defined as the date of last dose of IP + 29 days.

Listings of non-drug treatment(s)/procedure(s) and concomitant medication(s) will be provided (see Section 6.6.3). These will be blinded tables and will be reviewed prior to database lock to determine which procedures and medications would be classed as "prohibited".

Participants who are randomized to the wrong stratum, in error, will have the incorrect stratum assignment remain in IMPALA but the clinical database will include the correct stratum. The latter will subsequently be used for all relevant analyses, as appropriate.

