5.2.7. Cox Proportional Hazards Model

The Cox proportional hazards model will include treatment as a fixed term in the model. Additional terms will be fitted in the model (eg, type of therapy [ie, platinum or not], type of cancer), as appropriate. Hazard ratios versus placebo (and 90% CIs and p-value) will be provided. No adjustments will be made for multiplicity. If the model is deemed inappropriate (e.g. the assumption of proportional hazards is not met), the analysis may not be performed.

Standard SAS output will be provided to support the statistical summary table for the analysis model.

Example SAS code is provided in Appendix 4.

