6. ANALYSES AND SUMMARIES

Unless otherwise specified, all analyses will be carried out using the Censored Analysis Set as defined in Section 4.

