6.4.12. Survival status at end of Part A

Survival status at the end of Part A (Week 12) will be summarized descriptively by treatment group and overall, as described in Section 5.2.2.

Time to death will be summarized descriptively by treatment group, as described in Section 5.2.1. A cumulative incidence plot, as described in Section 5.2.6 will also be produced. Time to death will be analyzed using a Cox-proportional hazards model, as described in Section 5.2.7. All deaths will additionally be listed.

6.4.13. Response as defined by a ≥3.5% increase from baseline in body weight at Week 12

Response as defined by a ≥3.5% increase from baseline in body weight will be summarized descriptively by treatment group and timepoint, as described in Section 5.2.2, with no imputation for missing data, including all post-baseline timepoints up to Week 12 (ie. Weeks 4, 8 and 12). Barcharts of the percentages over time will also be produced, with all treatments on the same plot.

The percentage of responses (and 90% CIs) at Week 12 will also be reported by treatment after multiple imputation for missing values as per Section 5.3.1. These responses will also be analyzed separately using a logistic regression model (as described in Section 5.2.8), where missing values will be imputed using multiple imputation as per Section 5.3.1. The logistic regression model will be fitted to the data at Week 12 only.

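### The time-to-death curve censors at the end of study treatment (last dose + 29 days), so known Part A deaths after that date in participants who stop early are left out

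*SAP*

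**What the plan says.** - **Censoring rule (SAP 5.2.6):** "Participants who discontinue from the study or from study intervention will be censored at the associated discontinuation date". The example code in SAP Appendix 4 describes a censoring indicator but not how it is set, so this sentence is the only definition.
- **Date (SAP 4):** "the date of discontinuation of study intervention is defined as the date of last dose of IP + 29 days".
- **Use (SAP 6.4.12):** within the survival section, "A cumulative incidence plot, as described in Section 5.2.6 will also be produced". No other section calls for this plot, and no exception is made for death.
- **Endpoint (SAP 3.4.12):** "The time (days) to death during Part A (up to Week 12) will also be calculated for each participant". Survival status at Week 12 is also recorded for each participant.
- **Follow-up (Protocol 7.1):** "If study intervention is permanently discontinued, the participant should remain in the study to be evaluated for follow up". The listed reasons for stopping include hospitalization that makes participation unfeasible and "Progression of underlying disease such that the investigator no longer considers participation appropriate, or of potential benefit to the participant".
- **Model (SAP 5.2.7, for the same endpoint):** "Hazard ratios versus placebo (and 90% CIs and p-value) will be provided". Its text states no censoring rule.
- **Default analysis set (SAP 6):** "Unless otherwise specified, all analyses will be carried out using the Censored Analysis Set as defined in Section 4". Section 6.4.12 names no other set.

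**The concern.** Death can be observed after treatment stops, and this plan arranges to observe it. Censoring at the end of treatment discards those observations. It also assumes that participants who stopped have the same later hazard as those still on treatment. When the stated reasons for stopping include progression and hospitalization, that assumption is hard to defend.

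If the hazard rises after stopping, the curve understates 12-week mortality. If one arm has more stopping followed by death, the difference between arms shrinks. The curve could also disagree with the by-arm Week 12 status table in the same section. The SAP treats death differently elsewhere: for the 3.5% weight responder endpoint (3.4.13), a participant who dies is a non-responder even if the weight value was censored earlier.

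The Cox model, and possibly the status table, would suffer the same loss only if the Section 6 default set is applied to them. The SAP does not settle this, so it is an ambiguity to resolve and not a demonstrated error.

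**Working it through.** **The plan's own figure.** Protocol 9.5 expects about 120 completers from 168 at about 30% discontinuation: 168 × 0.70 = 117.6, which agrees. The point disputes no stated number; the 30% is used below as an assumption.

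**Step 1: censoring days.** Doses fall on Days 1, 29 and 57, and Week 12 is Day 85 (protocol Schedule of Activities). Censoring day = last dose + 29.

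| Last dose | Censoring day | Part A days not counted |
|---|---|---|
| Dose 1, Day 1 | 30 | 85 − 30 = 55 |
| Dose 2, Day 29 | 58 | 85 − 58 = 27 |
| Dose 3, Day 57 | 86 | 0 |

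With the ±3-day visit window, dose 2 gives Days 55–61 (24–30 days lost) and dose 3 gives Days 83–89 (0–2 days lost). Deaths within 29 days of the last dose still count. The loss falls on participants who stop after dose 1 or 2.

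**Step 2: size under assumptions.** The documents give no death rate or post-stop hazard. Assumed ranges:
- on-treatment 12-week death risk r of 5% or 10%;
- stopping proportion p of 15% or 30%;
- post-stop hazard ratio HR of 1, 3 or 5.

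The on-treatment hazard is λ = −ln(1 − r)/84 per day (for r = 5%, 0.0513/84 = 0.00061). It is multiplied by HR after the stop. The plotted risk is the Kaplan–Meier value 1 − ∏(1 − d/n), with censoring at last dose + 29 capped at Day 85. Each scenario simulates 4,000,000 participants, with stops spread evenly over 12 weeks.

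| r | p | HR | True risk | Plotted risk | Deaths dropped | Dropped per arm of 42 |
|---|---|---|---|---|---|---|
| 5% | 15% | 1 | 5.0% | 5.0% | 4.8% | 0.10 |
| 5% | 15% | 3 | 5.7% | 5.3% | 12.2% | 0.29 |
| 5% | 15% | 5 | 6.4% | 5.5% | 17.4% | 0.46 |
| 5% | 30% | 1 | 5.0% | 5.0% | 9.7% | 0.20 |
| 5% | 30% | 3 | 6.4% | 5.6% | 21.7% | 0.58 |
| 5% | 30% | 5 | 7.7% | 6.1% | 28.4% | 0.92 |
| 10% | 15% | 1 | 10.0% | 10.0% | 4.8% | 0.20 |
| 10% | 15% | 3 | 11.3% | 10.5% | 11.5% | 0.54 |
| 10% | 15% | 5 | 12.5% | 11.0% | 15.8% | 0.83 |
| 10% | 30% | 1 | 10.0% | 10.0% | 9.6% | 0.40 |
| 10% | 30% | 3 | 12.7% | 11.1% | 20.5% | 1.09 |
| 10% | 30% | 5 | 15.0% | 12.1% | 26.5% | 1.67 |

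Hand check at HR 1 and p = 15%: one third of stops lose 55 of 84 days, one third lose 27 and one third lose none. That gives 0.15 × (55 + 27)/(3 × 84) = 4.9%, in line with the 4.8% in the table.

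**Step 3: early stopping.** If every stop occurs before dose 2, 10–47% of deaths are dropped (0.2–3.3 per arm). The largest understatement is 18.0% − 12.0% = 6.0 points (r = 10%, p = 30%, HR 5).

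**Step 4: comparison between arms.** Take r = 5% in both arms, 40% versus 20% stopping, and HR 3. True risks are 6.9% and 6.0%, a ratio of about 1.16. Plotted risks are 5.8% and 5.4%, a ratio of about 1.07 to 1.08. At HR 5 the ratio is 1.26 true and 1.14 plotted. At HR 1 both are 1.00.

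**Step 5: reading the 30% as total non-completion, on-treatment deaths included.** At HR 5, 27.4% of deaths are dropped with a 1.5-point understatement (r = 5%), or 22.2% with 2.3 points (r = 10%).

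**The case against.** The strongest case is that this is one descriptive figure for a tertiary endpoint with no estimand. The plot carries no test. Survival status is named for hypothesis testing in SAP 5.1, but the only p-value described for survival comes from the Cox model, whose text states no such censoring. By-arm Week 12 status, a summary of time to death and a listing of all deaths are also planned. An on-treatment curve is a legitimate display, and it resembles the adverse event window for participants not entering Part B, which closes 28–35 days after the last dose (SAP 3.2.4.1).

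The size is also modest and rests on assumed rates. With 42 per arm, the binomial standard error at a 6.4% risk is √(0.064 × 0.936/42) = 3.8 points. At 15% it is √(0.15 × 0.85/42) = 5.5 points. Both exceed the matching understatements of 0.8 and 2.9 points. The 30% planning rate concerns completion through Week 12, and some of those participants leave the study altogether. They would be censored under any rule, so the recoverable share of deaths is smaller than simulated.

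Most of this stands and limits the importance of the point. It does not rescue the rule. The SAP does not call the curve on-treatment or give that rationale. A listing does not correct a by-arm curve. Sampling error does not excuse a systematic understatement that known data would remove.

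**Conclusion.** The point holds and should be fixed. As written, the time-to-death curve omits known Part A deaths that occur more than 29 days after dose 1 or dose 2 in participants who stopped study treatment. Participants who receive all three doses are essentially unaffected.

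That deaths are lost follows from the text alone. The size of any bias does not. It depends on assumed mortality, stopping and post-stop hazard, and is zero if the hazard does not rise after stopping. With evenly spread stopping it reaches 2.9 points and 1.7 deaths per arm; if all stops come before dose 2, it reaches 6.0 points and 3.3 deaths per arm. Confidence is high for the plot. For the Cox model and the status table, the finding is only that the SAP leaves the analysis set and the censoring unclear.

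**What to change.** In SAP 5.2.6, 5.2.7 and 6.4.12, state that:

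- survival status and time to death are analysed in all dosed participants, naming the Safety or the Evaluable set;
- every known death to Week 12 counts, regardless of treatment discontinuation, missed dose or prohibited medication (the last two matter because the default Censored set also removes data after them);
- censoring occurs only at Week 12, study withdrawal or last date known alive.

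The present rule can be kept as a supplementary analysis labelled on-treatment.

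The cost is SAP wording and one derived censoring variable. Survival status to Week 12 is already recorded for each participant, so no new data are needed.

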5.2.7. Cox Proportional Hazards Model

The Cox proportional hazards model will include treatment as a fixed term in the model. Additional terms will be fitted in the model (eg, type of therapy [ie, platinum or not], type of cancer), as appropriate. Hazard ratios versus placebo (and 90% CIs and p-value) will be provided. No adjustments will be made for multiplicity. If the model is deemed inappropriate (e.g. the assumption of proportional hazards is not met), the analysis may not be performed.

Standard SAS output will be provided to support the statistical summary table for the analysis model.

Example SAS code is provided in Appendix 4.

5.2.8. Logistic Regression

The logistic regression model will include baseline and treatment as fixed terms in the model. Additional terms may be fitted in the model (eg, type of therapy [i.e. platinum or not] and type of cancer), as appropriate. Missing values (e.g. due to censoring) will be imputed for missing data using a multiple imputation method as described in Section 5.3.1. Odds (and 90% CIs) and odds ratios versus placebo (and 90% CIs and p-values) will be provided. No adjustments will be made for multiplicity.

Standard SAS output will be provided to support the statistical summary table for the analysis model and multiple imputation approach but will not be included in the CSR.

Example SAS code is provided in Appendix 4.

5.3. Methods to Manage Missing Data

For the analysis of safety endpoints, the sponsor data standard rules for imputation will be applied.

In all PD data presentations (except listings), concentrations below the limit of quantification (BLQ) will be set to the lower limit of quantification (LLQ).

In all PK data presentations (except listings), concentrations below the limit of quantification (BLQ) will be set to zero.

In listings, BLQ values (for PK or PD) will be reported as "<LLQ", where LLQ will be replaced with the value for the LLQ.

For PK and PD summary tables and plots of median profiles, statistics will be calculated having set concentrations to missing if one of the following cases is true:

- A concentration has been collected as ND (i.e. not done) or NS (i.e. no sample),
- A deviation in sampling time is of sufficient concern or a concentration has been flagged anomalous by the pharmacokineticist/statistician.

5.3.1. Multiple Imputation

For summarizing the proportion of responses (e.g. response as defined by a ≥3.5% increase from baseline in body weight at Week 12), all percent change from baseline data from the censored analysis set will be included (all timepoints up to and including Week 12, i.e. Weeks 4, 8 and 12). A multiple imputation method will be implemented, using a multivariate imputation method by chained equations, which is still valid with an arbitrary missing data pattern. The model will include baseline and treatment. Additional terms for type of therapy [i.e. platinum or not] and type of cancer will also be included, as appropriate. Twenty sets of imputations of each missing value will be constructed from the multiple imputation method and the proportion of responses by treatment will be determined with associated standard errors utilizing a normal approximation and will be combined using standard multiple imputation techniques proposed by Rubin² to yield overall estimates and CIs. If there is more missing data in the study than anticipated, the number of imputation sets may be increased as required. Note that data for participants who die during the study will be included in the imputation but will then be classed as having a 'Non-response' after imputation.

For logistic regression, all percent change from baseline data from the censored analysis set will be included (all timepoints up to and including Week 12, i.e. Weeks 4, 8 and 12). The same imputed datasets as produced for the proportion of responses above will be utilized, where a Logistic Regression model (as described in Section 5.2.8) will be applied to each of the 20 imputed datasets separately. Parameter estimates, of the log odds for each treatment and log odds ratios for each dose relative to placebo, will be combined using standard multiple imputation techniques proposed by Rubin² to yield overall estimates of the log odds and log odds ratios and their associated standard errors and will be used to create 90% CIs on the log-odds scale. The log odds (and CIs) and log odds ratios (and CIs) will be back transformed into odds and odds ratios (and CIs) for final reporting.

